7.14 Rationale of Endpoints Definition

Primary Endpoint:

Safety (acute and long term) will be evaluated using CTCAE version 4.03 in all patients who have received at least one SABR treatment and one dose of pembrolizumab. Acute adverse events (AE) are defined as AEs occurring from the time of first SABR treatment to 30 days post

end of pembrolizumab treatment and long term AE are defined as AEs occurring after 30 days post end of pembrolizumab treatment.

Secondary Endpoints:

To evaluate effectiveness of the treatment combination, using the following measures:

- a) Overall survival (OS), time to local progression (TTLP), distant progression free survival (DPFS) and overall response rates
 - i. OS will be measured from the date of commencement of SABR treatment to the date of death from any cause.
 - ii. TTLP will be measured from date of commencement of SABR treatment to the date of first local progression. Death and commencement of a further course of systemic therapy will be considered as censoring events.
 - iii. DPFS will be measured from the date of commencement of SABR treatment to the date of first distant progression at site not documented at registration, or date of death from any cause for patients without distant progression. Commencement of second course of a further course of systemic therapy will be considered as censoring event.
- b) Overall response is defined as complete response or partial response, measured using RECIST 1.1 criteria. The RECIST definition of complete response has been modified to include disappearance of the target tumor radiographically or complete metabolic response. The primary is excluded from the evaluation of the overall response.
- c) Disease control is defined as complete response or partial response at any time after treatment commencement or stable disease for at least 6 months, measured using RECIST 1.1 criteria. The RECIST definition of complete response has been modified to include disappearance of the target tumor radiographically or complete metabolic response. The primary is excluded from the evaluation of the disease control.
- d) Pain will be evaluated using the Numerical Pain Rating Scale at the following time points: pre-conventional radiotherapy treatment (if CRT performed), pre-SABR treatment, prior to each cycle of pembrolizumab, then 3 monthly until 24 months after the end of SABR treatment.

Exploratory Endpoints

A number of translational endpoints will be evaluated including:

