9.5 Participant Withdrawal/Discontinuation Criteria

9.5.1 Protocol Treatment Discontinuation

A participant must be discontinued from the trial treatment for any of the following reasons:

- The participant or legal representative (such as a parent or legal guardian) withdraws consent.
- Unacceptable adverse experiences as described in Section 9.1.18: Dose Modifications
- Intercurrent illness that prevents further administration of treatment
- Investigator's decision to withdraw the participant
- The participant has a confirmed positive serum pregnancy test
- Noncompliance with trial treatment or procedure requirements

When a participant discontinues/withdraws treatment prior to trial completion, all applicable activities scheduled for the End of Treatment visit should be performed at the time of discontinuation. Any AEs which are present at the time of discontinuation/withdrawal should be followed in accordance with the safety requirements. After discontinuing treatment (for any reason), participants should attend the site for a 30 day (post end of trial treatment) safety follow-up visit (see Section 10.3) for assessment of AEs and Efficacy.

The End of Treatment and Follow-up visit procedures are listed in The Schedule of Events (Section 2) and Section 10.2: Visit Requirements. After the end of treatment, each participant will be followed for 30 days for adverse event monitoring (serious adverse events will be collected for 90 days after the end of treatment as described in Section 10.8.5 Serious Adverse

Events. Participants who discontinue treatment will have post-treatment follow-up for disease status until initiating a non-study systemic cancer treatment, withdrawing consent or becoming lost to follow-up.

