10.1.16 Subsequent Anti-Cancer Therapy Status

The investigator or qualified designee will review all new anti-neoplastic therapy initiated after the last dose of trial treatment. If a participant initiates a new anti-cancer therapy within 30 days after the last dose of trial treatment, the 30 day Safety Follow-up visit must occur before the first dose of the new therapy. Once new anti-cancer therapy has been initiated the participant will move into survival follow-up.

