10.3 Safety Follow-Up Visit

The mandatory Safety Follow-Up Visit should be conducted 30 days \pm 3 days after the last dose of trial treatment or before the initiation of a new anti-cancer treatment, whichever comes first. All AEs that occur prior to the Safety Follow-Up Visit should be recorded. Participants with an AE of Grade > 1 will be followed until the resolution of the AE to Grade 0-1 or until the beginning of a new anti-neoplastic therapy, whichever occurs first. SAEs that occur within 90 days of the end of treatment or before initiation of a new anti-cancer treatment should also be followed and recorded.

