10.8.1 Adverse Event Reporting

All adverse events will be recorded from the time the consent form is signed through 30 days following completion of pembrolizumab treatment. SABR related adverse events will be followed at each follow-up visit until 2 years after completion of SABR.

All adverse events, which occur whilst the participant is enrolled on the trial (including the follow-up phase), must be reported in the patients' medical records and recorded on the Adverse Events CRF. The Common Terminology Criteria for Adverse Events (CTCAE version 4.03 – see appendices) or other more specific AE tools must be used to grade the severity of an event. Laboratory values need reporting as AEs only if abnormal and deemed clinically significant by the investigator

All adverse events must be recorded on the Adverse Events CRF with the following information:

- The severity grade using CTCAE version 4.03
- Its relationship to the study drug(s)
- Treatment changes
- Whether it constitutes a serious adverse event (SAE)

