Any serious adverse event, or follow up to a serious adverse event, including death due to any cause other than progression of the cancer under study that occurs to any participant from the time the consent is signed through 90 days following cessation of pembrolizumab treatment, or the initiation of new anti-cancer therapy, whichever is earlier, whether or not related to protocol treatment, must be reported within 24 hours to the Sponsor and within 2 working days to Merck Global Safety.

Additionally, any serious adverse event, considered by an investigator who is a qualified physician to be related to protocol treatment that is brought to the attention of the investigator at any time outside of the time period specified in the previous paragraph also must be reported immediately to the Sponsor and to Merck.

SAE reports and any other relevant safety information are to be forwarded to the Merck Global Safety [contact].

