10.8.5.3 Events of Clinical Interest

Selected non-serious and serious adverse events are also known as Events of Clinical Interest (ECI) and must be recorded as such on the Adverse Event case report forms/worksheets and

reported within 24 hours to the Sponsor and within 2 working days to Merck Global Safety. (Attn: Worldwide Product Safety; [contact]).

For the time period beginning when the consent form is signed until treatment commences, any ECI, or follow up to an ECI, that occurs to any subject must be reported within 24 hours to the Sponsor and within 2 working days to Merck Global Safety if it causes the subject to be excluded from the trial, or is the result of a protocol-specified intervention, including but not limited to washout or discontinuation of usual therapy, diet, placebo treatment or a procedure.

For the time period beginning at first treatment through 90 days following cessation of treatment, or 30 days following cessation of treatment if the subject initiates new anticancer therapy, whichever is earlier, any ECI, or follow up to an ECI, whether or not related to protocol treatment, must be reported within 24 hours to the Sponsor and within 24 hours to Merck Global Safety.

Events of clinical interest for this trial include:

1. an overdose of pembrolizumab, as defined in Section 10.8.3 Definition of an Overdose for This Protocol and Reporting of Overdose to the Sponsor, that is not associated with clinical symptoms or abnormal laboratory results.
2. an elevated AST or ALT lab value that is greater than or equal to 3X the upper limit of normal and an elevated total bilirubin lab value that is greater than or equal to 2X the upper limit of normal and, at the same time, an alkaline phosphatase lab value that is less than 2X the upper limit of normal, as determined by way of protocol-specified laboratory testing or unscheduled laboratory testing.*

*Note: These criteria are based upon available regulatory guidance documents. The purpose of the criteria is to specify a threshold of abnormal hepatic tests that may require an additional evaluation for an underlying etiology.

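### AE collection must run to 30 days after pembrolizumab (7.14, 9.5.1, 10.8.1), but 10.3, 10.1.16 and 10.4 leave no scheduled AE contact once a patient switches therapy early

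*Combined protocol and SAP*

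**What the plan says.** Four places give a 30-day window and make no exception for new therapy:

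- Section 7.14: "Acute adverse events (AE) are defined as AEs occurring from the time of first SABR treatment to 30 days post" the end of pembrolizumab.
- Section 10.8.1: "All adverse events will be recorded from the time the consent form is signed through 30 days following completion of pembrolizumab treatment".
- Section 9.5.1: every participant is monitored for adverse events for 30 days after treatment ends.
- Schedule of Events, note 2: AEs are assessed 30 days after the last pembrolizumab dose.

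Three sections and a Schedule note work differently for a patient who starts another treatment before day 30:

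- Section 10.3 puts the safety visit at 30 ± 3 days or "before the initiation of a new anti-cancer treatment, whichever comes first. All AEs that occur prior to the Safety Follow-Up Visit" are to be recorded. It also ends follow-up of AEs above grade 1 when new therapy begins.
- Section 10.1.16 requires the visit to precede the new drug and adds: "Once new anti-cancer therapy has been initiated the participant will move into survival follow-up".
- Section 10.4 and Schedule note 18 say that patients on a new systemic therapy are followed for survival only.

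Serious events and events of clinical interest (ECIs) have their own windows. Under 10.8.5, SAEs are reported for 90 days "or the initiation of new anti-cancer therapy, whichever is earlier, whether or not related to protocol treatment". Under 10.8.5.3, ECIs are reported for 90 days, "or 30 days following cessation of treatment if the subject initiates new anticancer therapy, whichever is earlier".

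Section 11.2.3 reports the maximum grade of each event and the grade 3+ proportion, with an exact 95% CI, in all treated patients. It has no rule for patients who switch. Section 11.2.2 intends no imputation.

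**The concern.** Safety is the only primary objective, and its main summary is a proportion over a stated window. If the visit plan does not observe that window in some patients, an event there counts as no event, because nothing is imputed and the patient remains in the denominator. A grade 2 event that worsens after the switch keeps its lower grade.

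Patients who switch within 30 days are likely to be those who progressed or stopped for toxicity, so any shortening depends on how they fared. The lost days are not free of risk: 9.1.18.2 says that pembrolizumab AEs can appear months after the last dose. Two sites could also record different events for the same patient, depending on whether they follow 10.8.1 or 10.3.

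**Working it through.** **1. The plan's own figures.** Table 8 (11.2.9) gives exact intervals for n = 30. The Clopper-Pearson limits are: lower = Beta quantile 0.025 with parameters (x, n − x + 1); upper = Beta quantile 0.975 with parameters (x + 1, n − x). For x = 6 this gives 20.0% (7.7% to 38.6%), which matches the stated 20% (8% to 39%). All 12 rows reproduce after rounding. The arithmetic of the plan is not in question.

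**2. The rules side by side, for a patient who starts new therapy on day d < 30 after the last dose.**

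| Question | 7.14, 9.5.1, 10.8.1, note 2 | 10.3, 10.1.16, 10.4, note 18 |
|---|---|---|
| Last day of AE collection | Day 30 | AEs asked for up to a visit on or before day d |
| Follow-up of AEs above grade 1 | No stop at new therapy stated | Stops at new therapy |
| Scheduled AE contact after day d | Implied by the 30-day duty | None; survival only |

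The days without a scheduled AE contact number at least 30 − d. For d = 10 that is 30 − 10 = 20 days. A non-serious grade 3 event on day 20 in that patient is inside the 7.14 window and must be recorded under 10.8.1, but no planned visit would find it.

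**3. What is still captured.** ECIs are kept to 30 days after a switch (10.8.5.3). Treatment-related SAEs are reportable at any time (10.8.5). SABR-related AEs have a two-year rule (10.8.1). Section 10.8.5 classes grade 4 and grade 5 events as serious. The exposed events at grade 3+ are therefore non-serious grade 3 events not related to SABR, and SAEs judged unrelated.

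**4. Size per patient.** One missed patient who is not already counted as grade 3+ moves the rate by 1/30 = 3.3 points. Taking 6/30 recorded as an example:

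| Missed patients | True count | Rate | Exact 95% CI |
|---|---|---|---|
| 0 | 6/30 | 20.0% | 7.7% to 38.6% |
| 1 | 7/30 | 23.3% | 9.9% to 42.3% |
| 2 | 8/30 | 26.7% | 12.3% to 45.9% |
| 3 | 9/30 | 30.0% | 14.7% to 49.4% |

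**5. Expected size.** The documents give neither the number of early switchers, s, nor the chance, q, that such a patient has a first grade 3+ event in the lost days. Both are assumptions. Expected understatement in points = 100 × s × q / 30.

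- s = 1, q = 0.02: 0.07 points
- s = 3, q = 0.05: 0.50 points
- s = 5, q = 0.10: 1.67 points

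A heavier set of assumptions has 3 to 6 patients switching on day 10 and a 30-day grade 3+ risk of 5% to 20%, so that 20/30 of the risk falls in the lost days:

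- 3 × 0.05 × 20/30 = 0.1 patients; 0.1/30 = 0.3 points
- 6 × 0.20 × 20/30 = 0.8 patients; 0.8/30 = 2.7 points

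This set treats every switcher as not yet counted and every grade 3+ event in the lost days as unrecorded, so its upper end is generous.

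**The case against.** A reader might infer that 10.3 closes the acute window at the visit for everyone who switches. The documents do not say so. Section 10.3 asks for AEs before the visit but does not state that later ones are left out. The duties in 9.5.1 and 10.8.1 are unconditional, and 10.8.1 also sends AEs from the follow-up phase to the CRF. This objection stands: a site that follows 10.8.1 loses nothing. What remains is that no scheduled contact exists through which to meet that duty.

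A reader might also infer that the SAE rules conflict, since 9.5.1 says that "serious adverse events will be collected for 90 days after the end of treatment". That sentence goes on to refer to 10.8.5, which sets the cut at new therapy, so there is no contradiction.

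On size, there are good reasons to expect few affected patients:

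- Patients who need immediate TKI therapy are excluded (8.4).
- Section 7.9 cites a similar population with a median of 14.1 months before systemic therapy.
- Section 10.1.17 asks for confirmation of progression 4 to 6 weeks later and allows pembrolizumab to continue meanwhile.
- In Table 6 most immediate permanent discontinuations are for grade 3 to 4 events, so those patients are already counted. Most other toxicity discontinuations depend on non-resolution within 12 weeks, when the 30-day window has passed.

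These points stand and keep the estimate low.

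Finally, stopping collection at the next drug limits contamination by that drug's toxicity. This is a legitimate choice of estimand, but it is not the one in 7.14, and 11.2.3 does not mention it.

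**Conclusion.** The documents contain an unreconciled conflict over data that feed the primary endpoint. If sites work from 10.3, 10.1.16 and 10.4, the acute grade 3+ proportion can be understated in patients who start new therapy before day 30. Patients who switch after day 30 are unaffected for the acute window.

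The effect is conditional on site practice and probably small: around or below 1 to 2 points in expectation, against an exact interval about 31 points wide at 6/30 (38.6 − 7.7 = 30.9). That range rests on assumed switching numbers and event risks. A single missed patient would still move the rate by 3.3 points. The documents do not support an established downward bias or a settled early closure of the window. The change is worth making because it is cheap and delivers the window that the protocol already states.

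**What to change.** - In 10.3, 10.1.16 and 10.4 (and Schedule note 18), keep the visit before new therapy. State that AE recording and grading continue to 30 days after the last pembrolizumab dose whether or not new therapy has started, with one telephone contact at day 30.
- Record the start date of the new therapy on the CRF.
- In 11.2.3, report the grade 3+ proportion over the full window, and again with events after the start of new therapy excluded.
- Consider giving SAEs in 10.8.5 and 10.8.5.1 the 30-day minimum that 10.8.5.3 already gives ECIs.

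The cost is protocol wording, one date field, one telephone call for each early switcher and one extra table. The drawback is that some post-switch events will be due to the new drug; the second tabulation shows how much this matters. Nothing in the change affects treatment.

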10.4 Follow-up Visits

Participants who discontinue trial treatment for a reason other than disease progression will move into the Follow-Up Phase and should be assessed every 3 months by radiologic imaging to monitor disease status until the last evaluable patient completes 12 months of follow-up. Every effort should be made to collect information regarding disease status until the start of new systemic therapy, death, end of the study or if the participant begins retreatment with pembrolizumab as detailed in Section 10.6: Second Course Phase. Information regarding post-study anti-neoplastic treatment will be collected if new treatment is initiated. Participants who start a new systemic therapy, are retreated with pembrolizumab or have distant progression will be followed for survival only.

Participants who are eligible to receive retreatment with pembrolizumab according to the criteria in Section 10.6 Second Course Phase will move from the follow-up phase to the Second Course Phase when they experience disease progression.

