Whole Blood Sample ^{15,16}		X	X	X		X (9, 12 and 24 months)	X

Clinical/Administrative Assessments

- Vital signs include blood pressure, heart rate, respiratory rate and temperature. Height will be measured at screening only.
- Baseline abnormalities (using CTCAE v4.03) must be recorded from signature of informed consent to prior to start of treatment. Adverse events (using CTCAE v4.03) are then required to be assessed on day 1 of every pembrolizumab cycle and at 30 days following last pembrolizumab treatment. SABR related adverse events will be collected at every subsequent follow-up visit until 2 years after completion of SABR.

3. Conventional hypofractionated radiotherapy of **30-36Gy** may be delivered to individual lesion(s) if SABR is determined to be not technically or safely possible to deliver. If CRT is required it must be completed prior to SABR administration. **At least one lesion must receive SABR.**

4. Pembrolizumab should be administered at 5 days (+/- 3 days) of the last SABR treatment for a total of 8 cycles.

Laboratory Procedures/Assessments – All diagnostic laboratory tests should be performed within 10 days of study registration (to determine eligibility), and also within 3 days prior to every cycle of pembrolizumab (unless indicated otherwise below)

5. Urine or serum pregnancy test for patient of childbearing potential should be performed within 7 days of study registration and also 72 hours within first dose of pembrolizumab. If the urine test is positive or cannot be confirmed as negative, a serum pregnancy test will be required.

6. Haematology: Haematocrit, haemoglobin, platelet count, white blood cell count (total and differential), red blood cell count, absolute neutrophil count and absolute lymphocyte count.

7. Chemistry: Carbon dioxide (if considered standard of care only), uric acid, calcium chloride, glucose, phosphorus, potassium, sodium, magnesium, total protein.

8. Liver Function Tests: Albumin, Alkaline Phosphatase (ALP), Alanine Aminotransferase (ALT), Aspartate Aminotransferase (AST), Lactate Dehydrogenase (LDH), Gamma-Glutamyl Transferase (GGT, total bilirubin and direct bilirubin if total bilirubin is elevated above the ULN), Kidney Function Tests: Urea, creatinine.

9. Thyroid Function: T3, T4 and TSH.

10. Coagulation Profile: PT (INR), aPTT. These need only be done if there is clinical concern regarding patient anticoagulation.

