17. Study Follow-Up Visits - follow-up assessments (e.g visits @ 1, 3, 6, 9, 12, 15, 18, 21 and 24 months post end of SABR Treatment) should be undertaken within \pm 14 days of the scheduled time point. In the event of overlapping visits (i.e. between day 1 of each pembrolizumab cycle and post-SABR follow-up visits), only one visit is required but all protocol mandated investigations (for both timepoints) must be undertaken.

18. All patients will be followed for survival until the last evaluable patient completes 12 months of follow-up. Participants who start a new systemic therapy, are retreated with pembrolizumab or who have distant progression will be followed for survival only.

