- Does not have a history or current evidence of any condition, therapy, or laboratory abnormality that might interfere with the participant's participation for the full duration of the trial or is not in the best interest of the participant to participate, in the opinion of the treating investigator.

Participants who restart treatment will be retreated at the same dose and dose interval as when they last received pembrolizumab. Treatment will be administered for up to one additional year. Management of all immunotherapy related toxicities are outlined in Section 9.3.1 Supportive Care Guideline. This guideline should be followed in the retreatment period, however, any prior events and subsequent interventions or treatment modification during the initial treatment period should be continued in the retreatment phase. Any patient having sustained immunotherapy induced severe (grade 3) pneumonitis/ colitis / haematologic events etc. corticosteroids for > 12 weeks, or life-threatening events should be excluded from retreatment.

Once any new systemic anti-cancer therapy or, second course of pembrolizumab has been initiated, the participant will have concluded their participation in the treatment phase of the study. On completion of the treatment phase of the study the participant enters the follow-up phase and will be followed up for survival from the date any new treatment starts.

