10.8.2 Late Toxicities

Late toxicities (AEs) which are deemed by the investigator to be attributed to protocol specified SABR treatment are to be reported on the AE CRF. Late Toxicities are defined as AEs directly attributed by the Investigator to SABR treatment on this study, recorded from 30 days post last MK-3475 treatment until 24 months following the last SABR treatment.

10.8.3 Definition of an Overdose for This Protocol and Reporting of Overdose to the Sponsor and to Merck

For purposes of this trial, an overdose of pembrolizumab will be defined as any dose of 1,000 mg or greater (≥ 5 times the indicated dose). No specific information is available on the treatment of overdose of pembrolizumab. Appropriate supportive treatment should be provided if clinically indicated. In the event of overdose, the participant should be observed closely for signs of toxicity. Appropriate supportive treatment should be provided if clinically indicated.

If an adverse event(s) is associated with ("results from") the overdose of pembrolizumab, the adverse event(s) is reported as a serious adverse event, even if no other seriousness criteria are met.

If a dose of pembrolizumab meeting the protocol definition of overdose is taken without any associated clinical symptoms or abnormal laboratory results, the overdose is reported as a non-serious Event of Clinical Interest (ECI), using the terminology "accidental or intentional overdose without adverse effect" on the Adverse Event CRF page.

All reports of overdose with and without an adverse event must be reported within 24 hours to the Sponsor and within 2 working days hours to Merck Global Safety. (Attn: Worldwide Product Safety; [contact]).

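### Late SABR toxicity to 24 months belongs to the primary endpoint, but the survival-only rule removes its scheduled assessment for patients who progress or change therapy, and 11.2.3 still divides by all treated patients

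*Combined protocol and SAP*

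**What the plan says.** **Endpoint.** Section 7.14, under the primary endpoint: "Safety (acute and long term) will be evaluated using CTCAE version 4.03 in all patients" who had at least one SABR treatment and one pembrolizumab dose. Long-term events are those arising more than 30 days after pembrolizumab ends.

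**Window and means of collection.** Section 10.8.2 has late toxicities attributed to SABR "recorded from 30 days post last MK-3475 treatment until 24 months following the last SABR treatment", with no exception for progression or new therapy. The adverse event footnote to Table 1 says "SABR related adverse events will be collected at every subsequent follow-up visit until 2 years after completion of SABR"; 10.8.1 agrees: "SABR related adverse events will be followed at each follow-up visit until 2 years after completion of SABR".

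**Exit rule.** Section 10.4: "Participants who start a new systemic therapy, are retreated with pembrolizumab or have distant progression will be followed for survival only". Footnote 18 to Table 1 gives the same three triggers. For new therapy, 10.1.16 adds "Once new anti-cancer therapy has been initiated the participant will move into survival follow-up". For new therapy or a second pembrolizumab course, 10.6 says the participant "will be followed up for survival from the date any new treatment starts".

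**Analysis.** Section 11.2.3 plans a maximum-grade table and the grade 3+ proportion, by toxicity and overall, with an exact 95% CI in all treated patients. It does not separate acute from late events and has no time at risk. Section 11.2.2 rules out imputation. Section 11.2.4 names Kaplan-Meier for TTLP, DPFS and OS only.

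**The concern.** The late part of the primary endpoint depends on follow-up visits, and the exit rule appears to end those visits for anyone who progresses distantly, starts another systemic drug or is retreated. The denominator does not change when they leave. A patient who exits at month 7 stays among the 30 and contributes no late event unless one reaches the investigator by another route. Events missed over a fixed denominator can only lower the reported proportion.

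This matters because safety is the primary objective, and 11.1 treats good tolerability as part of the evidence for a randomised study. Section 7.10 itself notes that earlier SABR safety studies were small and short because patients died of their disease. Ending late assessment at progression would bring part of that limitation into this trial. A wish to avoid confounding by later drugs does not explain the distant-progression trigger, since progression alone introduces no new drug.

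**Working it through.** **1. The plan's own figures.** Exact (Clopper-Pearson) intervals with n = 30 reproduce all twelve rows of Table 8. For example, 3/30 gives 2.1% to 26.5% (printed 2% to 27%) and 12/30 gives 22.7% to 59.4% (printed 23% to 59%). The stopping probability in 11.2.10 also reproduces: P(2 or more of 12 at 5%) = 0.1184, and 1 − (1 − 0.1184)² = 0.2227 (printed 22%). No printed figure is wrong; the question is which events reach the numerator.

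**2. Late window.** With eight doses it opens on day 5 + 7×21 + 30 = 182, about month 6, and closes at month 24, so it lasts 18 months.

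**3. Share still under adverse event visits, S(t).** The documents give no exit rate for this trial, so these curves are assumptions.
- A: 58% at 12 months and 33% at 24, piecewise exponential. These are the rates without systemic therapy in the observational cohort cited in 7.9, which was managed with local therapies only.
- B and C: single exponentials reaching 50% and 70% at 24 months.

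S(6) is 0.58^0.5 = 0.762 for A, 0.50^0.25 = 0.841 for B and 0.70^0.25 = 0.915 for C.

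**4. Patient-time without visits.** This is 1 minus the mean of S over months 6 to 24.

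**5. Late risk that would be seen.** For a true late grade 3+ risk p, take a constant hazard h = −ln(1 − p)/18, exit independent of toxicity, and capture only at visits. The observed risk is the integral over u from 0 to 18 of h·exp(−hu)·S(6+u).

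| | A | B | C |
|---|---|---|---|
| Mean S, months 6–24 | 0.518 | 0.656 | 0.803 |
| Patient-time lost | 48% | 34% | 20% |
| True 10% shows as | 5.2% | 6.6% | 8.0% |
| Expected events in 30 (3.0 with full follow-up) | 1.6 | 2.0 | 2.4 |
| P(none in 30), true 10% (4% with full follow-up) | 20% | 13% | 8% |
| P(none in 30), true 4% (29% with full follow-up) | 53% | 45% | 38% |

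The 4% row uses the top of the grade 3 to 4 range in 7.7.3.

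**6. If nobody exits before month 6.** Divide by S(6). The share remaining at 24 months becomes 0.33/0.762 = 43%, 0.50/0.841 = 59% and 0.70/0.915 = 77%.
- Observed time is 0.518/0.762 = 68%, 0.656/0.841 = 78% and 0.803/0.915 = 88%, so the loss is 32%, 22% and 12%.
- A true 10% shows as 5.22/0.762 = 6.9%, 6.59/0.841 = 7.8% and 8.04/0.915 = 8.8%.

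**7. If half of the otherwise missed events are still caught.** Average the observed and true risks. From step 5 this gives (5.22 + 10)/2 = 7.6%, then 8.3% and 9.0%. From step 6 it gives (6.9 + 10)/2 = 8.4%, then 8.9% and 9.4%.

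**8. Study closure.** Analysis 12 months after the last recruitment also leaves later patients short of 24 months. With cut-off uniform over 12 to 36 months (24 months' accrual plus 12), case A falls from 5.2% to 4.6%. Extra contacts cannot recover that time. Deaths are not modelled.

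**The case against.** A reader might infer that no adverse event contact remains after exit. The documents do not go that far. Section 10.6 places these patients in the follow-up phase, and 10.8.1 asks for all adverse events to be recorded in that phase. Table 1 has no survival-only column: survival status and adverse event review share the Follow-up column, and the Progression column carries one review. The exit sentence in 10.4 follows text on imaging and disease status, so it could be read as ending efficacy follow-up only. Section 9.5.1 does not end disease follow-up at progression, and 10.1.17 allows pembrolizumab, with review each cycle, to continue beyond it. Section 10.8.5 keeps related serious events reportable at any time. All of this stands as evidence of partial capture. It does not remove the conflict with survival-only follow-up, because sites could reasonably follow either text. Nor does serious-event reporting cover a grade 3 event that meets no seriousness criterion.

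A reader might also infer that the reported grade 3+ rate would be roughly halved. That is not supported. Section 11.2.3 plans an overall proportion that includes acute events, whose collection is largely intact, and it claims no 24-month late risk. Curve A comes from a cohort without pembrolizumab and lets about 7 of 30 patients (30 × 0.238) exit before month 6, although 9.1.16 bars other systemic agents during the six treatment months. Step 6 answers that point and still leaves a loss of 12% to 32%.

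Finally, if those who leave differ in toxicity risk, the independence assumption in step 5 fails, and censoring at exit would not fully correct the bias. That is fair, and it favours continued collection over an analysis-only repair.

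**Conclusion.** The concern holds for the late component of the primary endpoint. Late SABR toxicity to 24 months is required in all treated patients. The exit rule puts its scheduled assessment in doubt for those who progress or change therapy, and the planned proportion makes no allowance for this. The direction does not depend on the exit curve: missed events over a fixed denominator make the late profile look safer. Non-serious grade 3 late events are the most exposed; the acute component is much less affected.

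The size is illustrative. Across curves with 33% to 70% remaining at 24 months, with and without exits before month 6 and with capture only at visits, 12% to 48% of late-window patient-time lacks adverse event visits. A true 10% late risk shows as about 5% to 9%, and closer to 10% once serious-event reporting is counted. These figures assume constant hazard and exit unrelated to toxicity. Table 8, the sample size and the stopping rule are not in question. The change should be made, as it protects the primary objective at small cost.

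**What to change.** **Collection.** In 10.4, 10.1.16 and footnote 18 (with matching words in 10.6), state that SABR-related adverse event review continues every 3 months to 24 months after SABR, or to study closure, despite progression, new therapy or retreatment. A phone call combined with the survival contact is enough. Flag events with onset after a new drug.

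**Analysis.** In 11.2.3, report late grade 3+ toxicity separately from acute toxicity. Use cumulative incidence with death as a competing event, censor at the end of adverse event observation, and give the numbers under adverse event follow-up at 6, 12 and 24 months. If the sponsor prefers to stop collection at exit, say so and state that the estimate then assumes exit is unrelated to toxicity.

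**Cost.** Contacts number 30 × the sum of (1 − S(t)) at months 9, 12, 15, 18, 21 and 24: about 93 under curve A and 39 under curve C, before subtracting deaths and study closure. Attribution to SABR will be less certain after a new drug, hence the flag. Sample size and stopping rule do not change.
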